4.3 Patient Discontinuation/Withdrawal Criteria

Patients can withdraw from participation in this study at any time, for any reason, specified or unspecified, and without prejudice.

All treated patients must be withdrawn from the study due to the following reasons:

- Development of an adverse event (AE) that interferes with the patient's participation
- Initiation of non-protocol therapy
- Development of progressive disease (PD)
- Patient withdrawal of informed consent
- Delay of poziotinib administration for >28 days since last study drug administration
- Investigator decision
- Sponsor decision

- Lost to follow-up
- Pregnancy
- Death

The reason for the patient discontinuing study treatment or terminating from the study must be recorded on the case report form (CRF). Patients who discontinue treatment or who are withdrawn from treatment will return for an End-of-Treatment Visit 30 (± 5) days after the last dose of poziotinib or prior to beginning a new treatment, whichever is first. If death is recorded as the reason for study discontinuation, the cause of death should be recorded on the CRF. Patients not efficacy evaluable i.e. not completed at least 1 cycle of poziotinib treatment and have baseline and at least 1 post-baseline tumor response evaluation using RECIST, version 1.1 (and/or RANO for **Cohort 4**) will be replaced unless they have discontinued from treatment or from the study due to disease progression or probable disease progression (eg. clinical progression, initiation of new therapy) or due to toxicity.

5 STUDY PROCEDURES

Refer to the Schedule of Study Assessments and Procedures presented in [Appendix 1](#).

5.1 Screening

Informed Consent is to be obtained prior to the start of any protocol-specified assessments or procedures. The procedures and evaluations required for enrollment into the study are summarized below. All potential study patients will be screened, and eligibility determined prior to enrollment. The results of any procedures or laboratory assessments performed prior to the signing of Informed Consent as part of the site's routine standard of practice will be allowed for use as a Screening Assessment at the discretion of the Sponsor. This information is to be discussed with the Medical Monitor before the patient is enrolled in the study.

Patients must have disease that is resistant to or relapsed following available standard systemic therapy (according to NCCN or ASCO guidelines), or for which there is no standard systemic therapy or reasonable therapy in the physician's judgment likely to result in clinical benefit or if such therapy has been refused by the patient. Documentation of the reason must be provided for patients who have not received a standard therapy likely to result in clinical benefit.

All procedures are to be performed as outlined in [Appendix 1](#) prior to the start of study treatment, unless otherwise noted.

5.2 Patient Assignment

Confirmation of eligibility is to be received by the investigational site from Spectrum prior to enrollment of a patient. After a patient has signed the ICF, the Investigator or site staff should assign a Patient ID. The Patient ID will include two parts: the site number assigned by Spectrum will be comprised of 5 digits with a 2-digit alphabetic country code [Reference ISO 3166] followed by a 3-digit site specific numeric code and a hyphenated 3-digit patient sequential number, unique to a site, separated by a hyphen (i.e., US001-001).

A CRF will only be completed for patients who are enrolled and receive a Patient ID.

5.3 Timing of Assessments and Procedures

5.3.1 Screening Visit (Within 30 Days of Cycle 1, Day 1)

The following screening assessments should be performed within 30 days prior to **Cycle 1, Day 1**. Obtain Informed Consent prior to any study procedures.

- Informed Consent
- Patient ID
- Relevant medical history
- Demographic data
- Height and weight
- Complete physical examination
- Vital signs
- Eastern Cooperative Oncology Group (ECOG) Performance Status assessment
- Pregnancy test (blood beta-human chorionic gonadotropin [β -HCG]) in women of childbearing potential
- Tumor assessment: **Screening** tumor assessment for patient eligibility will be based on scans performed locally within 30 days before the patient signed the ICF; **Baseline** tumor assessment (either CT, PET/CT, or MRI for non-brain organs and brain MRI) will be performed within 2 weeks prior to, or on **Cycle 1, Day 1**
- Tumor histopathology report (from local pathologist) and molecular test report for mutation diagnosis
- Complete blood count (CBC) with 5-part differential and platelets prior to poziotinib administration (may be obtained up to 7 days prior to **Cycle 1, Day 1**)
- Serum chemistry prior to poziotinib administration (may be obtained up to 7 days prior to **Cycle 1, Day 1**)
- Electrocardiogram (ECG)
- Echocardiogram or MUGA scan to evaluate cardiac ejection fraction (only for patients who have a high risk of cardiac disease, as determined by the Investigator)
- Tissue sample (from archival or fresh biopsy) or plasma for tumor genotyping
- Plasma sample for biomarker analysis
- Whole blood sample for pharmacogenomic analysis
- Adverse event assessment using NCI CTCAE, version 5.0. Only study-related SAEs to be recorded during **Screening**
- Concomitant medication review

5.3.2 Treatment Period – Cycle 1, Day 1

- Eligibility confirmation
- Height and Weight
- Physical examination
- Vital signs

- ECOG Performance Status assessment
- Urine pregnancy test in women of childbearing potential (if Screening pregnancy test was more than 7 days prior to **Day 1**)
- CBC with 5-part differential and platelets
- Serum Chemistry
- Intense pharmacokinetic sampling (see schedule of sampling in [section 5.4.6](#))
- ECG before each PK sampling
- Dispense poziotinib and loperamide
- Adverse event assessment using NCI CTCAE, version 5.0
- Dispense Patient Diary
- Concomitant medications review

5.3.3 Treatment Period – Cycle 1, Days 8 and 15 (±3 Days)

- Physical exam
- Vital signs
- Complete blood count with 5-part differential and platelets
- Intense pharmacokinetic sampling can occur only on C1D8 +/- 3 days (see schedule of sampling in [section 5.4.6](#))
- ECG before each PK sample on Day 8 only
- Adverse events using NCI CTCAE, Version 5.0
- Patient Diary Review
- Concomitant medications review
- Contact patient by telephone calls between Day 3- 8 for any AE, such as skin rash and diarrhea, and take action according to [Appendices 3, 4, and 5](#)

5.3.4 Treatment Period – Cycle 1, Day 22 (±2 Days) (By Telephone)

- Adverse event assessment using NCI CTCAE, Version 5.0
- Concomitant medications

5.3.5 Treatment Period – Cycle 2, Day 1

- Height and Weight
- Physical examination
- Vital Signs
- ECOG Performance Status assessment
- Urine pregnancy test in women of childbearing potential
- Tumor assessment: either CT, PET/CT, or MRI for non-brain organs and brain MRI (the same imaging acquisition method as the baseline should be used)
- Complete blood count with 5-part differential

- Serum chemistry
- Plasma sample for biomarker analysis
- Dispense poziotinib and loperamide
- Adverse event assessment using NCI CTCAE, Version 5.0
- Dispense and Collect Patient Diary
- Concomitant medications review

5.3.6 Treatment Period – Cycle 2, Day 8 (± 1 Day)

- Complete blood count with 5-part differential and platelets
- Adverse event assessment using NCI CTCAE, Version 5.0; a telephone call to patient for the follow up of AEs between Days 3 to 8
- Patient Diary review
- Concomitant medications review

5.3.7 Treatment Period – Cycle 3+, Day 1

- Weight
- Physical examination
- Vital Signs
- ECOG Assessment
- Urine pregnancy test in women of childbearing potential
- Tumor assessment: either CT, PET/CT, or MRI for non-brain organs and brain MRI (unless the patient has documented disease progression or has undergone a tumor assessment with the previous 8 weeks; the same imaging acquisition method as the baseline should be used)
- Complete blood count with 5-part differential
- Serum chemistry
- Plasma sample for biomarker analysis
- Dispense poziotinib and loperamide
- Adverse event assessment using NCI CTCAE, Version 5.0
- Dispense and Collect Patient Diary
- Concomitant medications review

5.3.8 End-of-Treatment Visit (30 [± 5] Days After Last Dose of Study Treatment)

The **End-of-Treatment Visit** is required 30 (± 5) days after the last dose of poziotinib is administered. The following assessments are to be performed at this visit:

- Height and Weight
- Physical examination
- Vital signs

- ECOG Performance Status assessment
- Urine pregnancy test in women of childbearing potential
- Tumor assessment (either CT, PET/CT, or MRI for non-brain organs and brain MRI (unless the patient has documented disease progression or has undergone a tumor assessment within the previous 8 weeks; same imaging acquisition method as the baseline should be used)
- CBC with 5-part differential and platelets
- Serum chemistry
- Newly biopsied tumor tissue taken from patients who progress for biomarker analysis (optional, but encouraged)
- Plasma sample for biomarker analysis if the patient progresses (optional)
- Adverse event assessment using NCI CTCAE, Version 5.0
- Patient Diary Collection
- Concomitant medications review

5.3.9 Long-Term Follow-up – Every 3 Months

- After progressive disease is documented, regardless of possible treatment continuation, patients who have consented will be contacted by phone or email (or letter if specifically requested) every 3 months, for up to 2 years after patient's first dose of poziotinib, for survival assessment
- Record SAEs where a causal relationship with the study drug is suspected.

5.4 Description of Study Assessment Parameters

5.4.1 Relevant Medical History

At **Screening Visit**, the patient's relevant medical history will be collected, to include previous therapy, as well as significant and relevant past diseases and current medications.

5.4.2 Physical Examination

A complete physical examination, including a description of external signs of the neoplastic disease and co-morbidities, will be performed at **Screening Visit, Cycle 1, Days 1, 8, and 15** and **Day 1** of each subsequent cycle, and **Day 1 of each cycle**, and at the **End-of-Treatment Visit**. Symptom-directed examinations are required at other visits. Physical examinations are to be completed by a physician or other health professional licensed to perform such examinations. Findings will be documented in the patient's medical record and on the appropriate CRF pages. Any abnormalities are to be recorded on the AE CRF.

5.4.3 Vital Signs

Vital signs, to include temperature, blood pressure, heart rate, and respiratory rate, are to be recorded at **Screening, Cycle 1, Days 1, 8, and 15** and **Day 1** of each subsequent cycle and at the **End-of-Treatment Visit**. Heart rate and blood pressure will be recorded before poziotinib administration.

5.4.4 ECOG Performance Status

Patients' Performance Status will be evaluated using criteria as developed by the Eastern Cooperative Oncology Group ([Appendix 2](#)) at Screening and Day 1 of each cycle and at the End-of-Treatment Visit.

5.4.5 Clinical Laboratory Tests

A local laboratory will be used to process all clinical specimens. The following clinical laboratory parameters will be evaluated in this study:

- **Complete Blood Count (CBC):** A CBC, including white blood cells (WBC), with 5-part differential, hemoglobin, and platelets will be performed at Screening, Day 1 and Day 8 of Cycle 1 and Cycle 2, Day 1 of each cycle, and at the End-of-Treatment Visit. The results of the laboratory assessments should be evaluated and medically accepted by the responsible physician before the start of each cycle.
- **Chemistry Panel:** A comprehensive chemistry and electrolytes, including blood urea nitrogen (BUN), AST/SGOT, ALT/SGPT, alkaline phosphatase (ALP), total bilirubin, albumin, calcium, lactate dehydrogenase, sodium, potassium, chloride, phosphate, magnesium, creatinine, uric acid, and glucose, will be performed at Screening Visit, Day 1 of each cycle, and at the End-of-Treatment Visit.
- **Special note for the Day 1 sampling of each cycle:** If possible, blood samples should be drawn on **Day 1** of each cycle (prior to treatment); however, for logistical reasons, it is also acceptable to draw samples for assessment up to 7 days prior to the start of a cycle. The results of the laboratory assessments should be evaluated and medically accepted by the responsible physician before the start of each cycle.
- **Pregnancy Test:** A blood β -hCG test will be performed for all women of childbearing potential at **Screening**. A urine pregnancy test is required on Day 1 of each Cycle starting from **Cycle 2** and at **Cycle 1, Day 1**, if Screening pregnancy test was more than 7 days prior to **Day 1**. Urine pregnancy test also required at **End-of-Treatment Visit**.

5.4.6 PK Sample

At select study centers, up to 25 patients may be specifically consented for intensive PK sampling and concurrent ECGs as defined below:

Schedule: Intensive PK blood sampling will be at pre-dose and 2, 4, 8, 12, and 24 hours post-dose on **Cycle 1, Day 1** and on **Cycle 1, Day 8 (± 3 days)**. The 12-hour and 24-hour PK samples must be collected prior to the second daily dose. A local 12-lead ECG will be obtained just before each PK blood sample on both Day 1 and Day 8. If the patient has interrupted continuous poziotinib dosing, clear dosing documentation must be done in order to assess suitability of further PK sampling and ECG recording.

In addition, if a patient presents with a potentially drug-related Grade ≥ 3 AE, a PK sample should be collected as soon as possible, if feasible, following the onset of the AE in order to characterize the PK. Documentation of last dose timing prior to the event is required.

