Official Title: A Phase 2 Study of Pozotinib in Patients with EGFR or HER2 Activating Mutations in Advanced Malignancies

NCT Number: NCT04172597

Document Date: Protocol Amendment 1: 20 May 2021

Study Title: **A Phase 2 Study of Poziotinib in Patients with EGFR or HER2 Activating Mutations in Advanced Malignancies (SPI-POZ-203)**

Protocol Version/Date: Amendment 1/20 May 2021

Deletions below are marked with red strikethrough text and additions are marked with red underlined text.

Summary of Significant Changes to the Protocol

Section	Change
Throughout Document	Minor edits for grammar, spelling, consistency, and typos.
Throughout Document: General Explanation	
Primary Changes:
 
 1. The starting poziotinib dosing regimen changed from 16 mg QD to 8 mg twice per day (BID). 
 • The 8 mg BID dose has demonstrated improved tolerability and retained or improved efficacy as the 16 mg QD dose. 2. The End-of-Treatment Visit was changed from 35 (±5) days to 30 (±5) days. 
 • 30 days for the End-of-Treatment Visit is the standard for clinical studies at investigational sites. 3. A long-term follow-up period was added for survival assessment for up to 2 years. 
 • Allows for the collection of additional outcome data. 4. Poziotinib dose modifications were altered to include dose reductions for BID dosing and Table 2 was revised. 5. Eligible patients who elect to continue treatment with poziotinib after disease progression in this study in will transition to an Extension Study (SPI-POZ-501). 6. At selected sites, intensive pharmacokinetic assessments have been added for up to 25 patients. 
 • This sampling will allow the required PK analyses for 8-mg BID dosing.
Title Page Footer Synopsis	
Original Text: Protocol Version/Date: Original/19-Sep-2019-Final
 
New Text: Protocol Version/Date: Amendment 1/20 May 2021

Section	Change				

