10. Patient has a high risk of cardiac disease, as determined by the Investigator. If patient is deemed to have a high cardiac risk, enrollment may be considered if echocardiogram (ECHO) or multi-gated acquisition (MUGA) during **Screening** demonstrates a cardiac ejection fraction >50%.
11. Patient has a QTc > 470 ms.
12. Patient has a history of other malignancies within the last 1 year, except for non-melanoma skin cancer, carcinoma in situ of the cervix, or PSA-stable, asymptomatic early stage prostate cancer or superficial bladder cancer without active treatment.
13. Patient has clinically significant or recent acute gastrointestinal disease presenting as diarrhea and/or colenteritis as the main symptom (i.e. acute enteritis, malabsorption, or Common Terminology Criteria for Adverse Events (CTCAE, version 5.0) Grade 2 or higher diarrhea due to other drug-related reasons within 15 days.
14. Patient is unable to take drugs orally due to disorders that may affect gastrointestinal function or has malabsorption syndrome.
15. Patient has an active liver disease or biliary tract disease (except for Gilbert's disease, asymptomatic biliary stones, liver metastasis, or stabilized chronic liver disease).
16. Patient has a medical condition that in the opinion of the investigator or medical monitor would put her/him at an unreasonable risk during the trial
17. Patient has known hypersensitivity to poziotinib or history of allergic reactions attributed to a compound of similar chemical composition to poziotinib.
18. Patient has an active or uncontrolled infection, active bleeding disorder, any underlying medical condition, or other serious illness that would impair the ability of the patient to receive protocol treatment.
19. Patient has had recent major surgery or invasive procedure within 15 days prior to starting study treatment.
20. Patient is pregnant or breast-feeding.

Investigational Product, Dose, and Route of Administration:

Poziotinib is supplied as 8-mg tablets and 2-mg tablets. The starting dose of poziotinib is 8 mg, twice per a day (BID). Patients will self-administer poziotinib orally with food and a glass of water, at approximately the same times each day (recorded in a diary). The first dose should be taken in the morning and the second dose should

be taken approximately 8 to 12 hours later. If a dose is missed, it should be taken once remembered or with the next dose if on the same day.

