6.1.2 Poziotinib Administration

Poziotinib is supplied as 8-mg and 2-mg tablets and will be administered on an outpatient basis orally twice daily.

Dosing Regimen

The starting dose of poziotinib is 8 mg twice per a day (BID). Poziotinib will be self-administered by the patient orally, with food and a glass of water, at approximately the same time(s) each day during each 28-day cycle.

The first dose should be taken in the morning and the second dose should be taken approximately 8 to 12 hours later. If a dose is missed, it should be taken once remembered or with the next dose if on the same day.

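### The timing rule for the 24-hour PK sample does not fit twice-daily dosing: it either requires an evening dose to be held, which no text instructs, or it constrains nothing

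*Combined protocol and SAP*

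**What the plan says.** Section 5.4.6 offers an optional intensive PK substudy to no more than 25 patients at selected centers. Blood is drawn before dosing and at 2, 4, 8, 12 and 24 hours after it, on Cycle 1 Day 1 and again on Day 8 (±3 days), with an ECG just before each draw. The timing rule is: "The 12-hour and 24-hour PK samples must be collected prior to the second daily dose". The same sentence stands in four other current places: the Synopsis under Pharmacokinetic Assessments, footnote o of the Synopsis schedule, Section 5.4.7, and footnote o of the Appendix 1 schedule.

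The dosing text, in Section 6.1.2 and twice in the Synopsis, is: "The first dose should be taken in the morning and the second dose should be taken approximately 8 to 12 hours later". Doses are taken "at approximately the same times each day (recorded in a diary"), so the next morning's dose is due at about 24 hours.

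The summary of changes gives the purpose of the sampling: "This sampling will allow the required PK analyses for 8-mg BID dosing".

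**The concern.** One phrase governs two draws that are 12 hours apart, while two doses are due in every 24 hours. The dose that decides what a 24-hour sample measures is the next morning's, because it is due at about the same time as the draw. The rule does not mention that dose.

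Three kinds of sample could be labeled 24-hour, depending on how a site reads the text:

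- evening dose held: 24 hours after the last dose, which is not a twice-daily profile;
- evening dose taken, draw before the morning dose: a trough, 12 to 16 hours after the evening dose;
- evening dose taken, draw just after the morning dose: a sample early in a new dosing interval.

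Pooling these at one nominal time would blur the PK summary and its paired ECGs. Section 5.4.6 explicitly requires dose-time documentation only after interrupted dosing and for samples triggered by an adverse event ("Documentation of last dose timing prior to the event is required").

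**Working it through.** The plan gives no count of PK samples and no PK precision target, so there is no figure to reproduce.

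**Inputs**

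- Patients: at most 25 (Section 5.4.6).
- Sampling times per PK day: 6 (pre-dose, 2, 4, 8, 12, 24 h; Section 5.4.6).
- PK days: 2 (Day 1 and Day 8; Section 5.4.6).
- Second dose: 8 to 12 h after the first (Section 6.1.2).
- Next morning's dose: about 24 h (same clock times each day; Section 6.1.2 and Synopsis).

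**Reading A: the second dose of the PK day**

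Lag of the draw behind the dose = 24 − time of second dose.

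- Second dose at 12 h: 24 − 12 = 12 h after it.
- Second dose at 8 h: 24 − 8 = 16 h after it.

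The draw follows the dose across the whole window. If the site also keeps the 12-hour part of the rule, the 12 h end applies. The rule is met only if the dose is held past 24 h.

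**Reading B: the second dose of the following day**

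Time of that dose = 24 + (8 to 12) = 32 to 36 h. The draw precedes it by 8 to 12 h whatever the site does. A draw taken after the next morning's dose would also comply.

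**The 12-hour sample**

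A draw at 12 h can precede a second dose taken at about 12 h, which lies inside the permitted window. The two texts are compatible here.

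**Does other text settle it?**

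The visit list for Cycle 1 Day 1 (Section 5.3.2) has "ECG before each PK sampling", and Section 5.3.3 has "Intense pharmacokinetic sampling can occur only on C1D8 +/- 3 days". Neither these lists nor the schedule tables have an entry for the day after a PK day, when the 24-hour draw falls. This is not a fault in itself, since footnote o and Section 5.4.6 fix the time, but it gives no help with the order of draw and dose.

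**Size**

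- Scheduled samples: 25 × 6 × 2 = 300 at most.
- 24-hour samples: 25 × 2 = 50 at most, and 50/300 = 16.7%.
- 24-hour samples in breach: 0 on reading B; up to 50 on reading A if the evening dose is not held.

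**The case against.** **The rule can be read literally.** The draws are fixed at 12 and 24 hours, so the dose must move: the evening dose is deferred until sampling ends. This is the strongest defense, and a hold is indeed the only way to comply on reading A. But the text never says to hold the dose, and a hold contradicts the 8 to 12 hour interval. It also fits poorly with sampling added to support PK at 8 mg twice daily, and the same rule applies on Day 8, during continuous twice-daily dosing. What stands is that a dose-free profile may have been wanted on Day 1, so the fix must leave room for it.

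**The phrase may mean the dose on the second day.** That would work for the 24-hour draw. However, Section 6.1.2 uses the term for the later dose of the same day, and the phrase must also cover the 12-hour draw.

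**Stronger readings that a reader might infer.** One is that the 12-hour samples are equally affected, because a second dose at 8 hours would put that draw 4 hours after it. The documents do not support this: the PK rule itself requires the dose to follow the draw, so dosing at 8 hours on a PK day would be non-compliance, not a conflict in the plan. Another is that the missed-dose instruction ("If a dose is missed, it should be taken once remembered or with the next dose if on the same day") forbids a hold. It addresses forgotten doses, and a dose deferred for a protocol draw is not one.

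**The harm is not shown.** This is partly right. Section 8 specifies no PK analysis, so no effect on a PK parameter can be calculated. The diary is dispensed on Day 1 and reviewed at Day 8, and should let samples be sorted afterwards. Sorting would not make them the same kind of sample.

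**Conclusion.** The point holds for the 24-hour sample. On one reading the rule cannot be met without holding a dose that nothing tells sites to hold; on the other it is empty and leaves the order of the draw and the next morning's dose undefined. At most 50 of 300 scheduled samples, with their ECGs, could be of mixed kinds. The number in formal breach runs from 0 to 50 according to the reading. These are maxima: they assume that all 25 places are filled and both PK days are completed, and they count scheduled samples only.

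A reader might go further and infer that the PK data as a whole would be unusable. The documents do not support that: the 0 to 12 hour interval is obtainable whenever the second dose follows the 12-hour draw.

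Severity is minor. The substudy is optional, PK is not among the objectives in Section 2, and the ORR analysis, the Simon stopping rules and the main safety summaries do not depend on it.

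**What to change.** Replace the sentence in all five places with: *On PK days the second dose is taken immediately after the 12-hour sample; the 24-hour sample is collected before the next morning's dose.* Record on the CRF the clock times of both PK-day doses and of the next morning's dose. All 24-hour samples (up to 50) could then comply and would be of one kind.

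If the sponsor instead wants a dose-free 24-hour profile on Day 1, the text should say explicitly that the evening dose is held that day. The replacement sentence would then apply to Day 8 only.

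The cost is one sentence in five places and three dose-time fields, with no added samples or visits. For participants, the second dose is fixed at about 12 hours on two days, still inside the permitted window, and the next morning's dose waits for the draw.
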